1.4.2 Sample size re-adjustment

1.4.2.1 STATISTICAL CALCULATION

The unadjusted proportions of primary endpoint response (after implementing the proxy imputation method defined above) will be used to calculate the sample size required in part B to achieve a 90% power.

[figure not shown]
The following SAS script will be used to obtain the required sample size:

```
proc power;
twosamplefreq test = pchi
groupproportions = (0.X 0.Y)
ntotal = .
power = 0.9;
run;
```

Figure 2 illustrates the distribution of the obtained required sample sizes vs. the observed treatment difference after using 100,000 simulations of part A trial (n = 20 per arm) assuming 20% rate with PBO and 50% rate with EFG.

SGS	Statistical Analysis Plan	
ARGX-113-2009	Final and Interim Analysis	Final 4.0 of 04NOV2024

Figure 2. Observed absolute difference in part A and resulting required sample size in part B

1.4.2.2 SAMPLE SIZE RE-ASSESSMENT ALGORITHM

[figure not shown]
The sample-size reassessment recommendation algorithm is as follows:

- If the obtained required sample size is smaller or equal to the sample size planned in the protocol (n = 120 for part B), then the sample size of part B will be maintained as planned in the protocol
- If the obtained required sample size is > 120, then part B sample size
 may be increased. This document acknowledges the possibility of not
 expanding the sample size of part B to the number obtained if that
 number is too large from a feasibility perspective

1.4.3 Control of the type I error for key secondary endpoints

1.4.3.1 STATISTICAL ANALYSIS

The following five key secondary endpoints will be analyzed at the IA as planned in Section 4.1.3:

- Normalized cumulative OCS dose (NCOD) over the on IMP treatment period
- Achieving a score of 0 on Investigator Global Assessment of Bullous Pemphigoid (IGA-BP) while receiving efgartigimod PH20 SC or placebo and have been off OCS therapy for ≥8 weeks at week 36
- Achieving control of disease activity (CDA) while receiving efgartigimod PH20 SC or placebo and remain free of relapse through week 36
- Achieving CR while receiving efgartigimod PH20 SC or placebo and have been receiving minimal OCS therapy for ≥8 weeks at week 36
- Change from baseline in the 24-hour average itch score

For each of the above key secondary endpoints, the primary estimand and primary estimator will be obtained only.

1.4.3.2 ALGORITHM TO ADAPT THE METHODOLOGY TO CONTROL TYPE I ERROR FOR KEY SECONDARY ENDPOINTS

The endpoints will be sorted in ascending order (i.e., smallest p-value first, largest p-value last). This order will be used in the final analysis of part B to test sequentially the key secondary endpoints (fixed sequence procedure).

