4.1.1. Description of Part A and Part B

A 2-part schematic of the overall study design is presented in Section 1.2; brief descriptions of both parts of ARGX-113-2009 are presented below:

Part A is a phase 2, proof-of-concept study in which approximately 40 adult participants with moderate-to-severe BP will be randomized in a 1:1 ratio to receive either efgartigimod PH20 SC or placebo. The main goal of part A is to determine whether efgartigimod PH20 SC is effective in the treatment of participants with BP via assessment of the study's primary endpoint: the proportion of participants who are in CR while receiving efgartigimod PH20 SC or placebo and have been off OCS therapy for ≥8 weeks at week 36. Other part A objectives and endpoints are listed in Table 3.

An interim analysis will be conducted from data obtained from all part A participants through the week 26 visit. The interim analysis will be conducted to assess the primary endpoint, assess several of the study's secondary endpoints, confirm the appropriate sample size for part B of the study, and determine whether the efficacy results observed through week 26 warrant continued study of efgartigimod PH20 SC for the treatment of participants with BP (futility analysis). The part A interim analysis is described in Section 9.4.

The final analysis of part A data will be performed after its last participant completes their last visit (Section 4.4).

Part B is a phase 3 confirmatory study in which approximately 120 adult participants with moderate-to-severe BP will be randomized in a 1:1 ratio to receive either efgartigimod PH20 SC or placebo. The main goal of part B is to confirm the results obtained for the primary endpoint from part A (the proportion of participants who are in CR while receiving efgartigimod PH20 SC or placebo and have been off OCS therapy for ≥8 weeks at week 36), but in a separate, larger group of participants with BP. Other part B objectives and endpoints are listed in Table 4. The proposed order of the key secondary endpoints for part B may be adjusted based on the results obtained from the part A interim analysis (Section 9.1.1).

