Part B is a phase 3, confirmatory study in which approximately 120 adult participants with moderate-to-severe BP will be randomly assigned to treatment with either EFG PH20 SC or PBO PH20 SC. The main goal of part B is to confirm the results obtained for the primary endpoint from part A (the proportion of participants who are in CR while receiving efgartigimod PH20 SC or placebo and have been off OCS therapy for ≥8 weeks at week 36), but in a separate and larger group of participants. Other part B objectives and endpoints are listed in section 1.1.2. The proposed order of the key secondary endpoints for part B may be adjusted based on the results obtained in the IA of part A of the study.

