4.1.2.3 PRESENTATION OF RESULTS

The primary endpoint will be analyzed on the FAS population and additionally on the PP population as sensitivity analysis.

A frequency tabulation will be provided for the disease status as collected in the CRF per analysis visit. This includes the status 'CR while being off OCS therapy for at least 8 weeks'. For participants who received rescue therapy, only assessments prior to or on the start date of rescue therapy will be considered.

Frequency tabulations will be provided of the percentage of participants who are in CR while receiving efgartigimod PH20 SC or placebo and have been off OCS therapy for ≥8 weeks at week 36 (composite strategy - primary endpoint). The table will be repeated for subgroups, including treatment differences in proportions with 95% Wald CI (with continuity correction).

The proportion of participants with BP who are in CRoff at week 36 will be tested by means of a Cochran-Mantel-Haenszel (CMH) test stratified for the 2 stratification factors of disease history (newly diagnosed versus relapsing) and disease severity as per IGA-BP at screening (moderate versus severe). The common (conditional) odds ratio will be provided, along with the exact 95% CI and 2-sided p-value from the CMH association test. In addition, the Klingenberg 95% CI for the strata-adjusted difference of proportions along with its midpoint estimate will be provided. Homogeneity of the odds ratios will be tested by means of a Breslow-Day test with Tarone's adjustment.

A sensitivity analysis will be performed on this primary endpoint using exact logistic regression with fixed effect terms for randomized treatment and stratified for the 2 stratification factors of disease history and disease severity as per IGA-BP at screening. Treatment groups will be compared in terms of the (conditional) odds ratio with 95% CI. A non-linear model with fixed effect terms for randomized treatment and the 2 stratification factors will be fitted to obtain the estimated treatment difference in proportions with 95% CI.

The same CMH test as for the primary analysis will be applied for the supplementary analysis (using a treatment policy strategy).

All sensitivity and supplementary analyses for the primary endpoint will be performed both for the analysis of study Part A, study Part B and pooled study Part A and B.

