4.1.3.2 Presentation of Results

1) Summary statistics on NCOD and (non-normalized) cumulative OCS dose (COD) will be provided.

An ANCOVA model with factors for treatment and the stratification variables will be applied on NCOD. Least square (LS) means and standard error (SE) with 95% 2-sided CI for placebo and efgartigimod will be reported, along with the difference in LS means of IMP vs placebo (with SE), 95% 2-sided CI, and 2-sided p-value.

The supplementary analysis (using the treatment policy strategy) will be analysed in a similar way (descriptive statistics and ANCOVA). This supplementary estimator is not considered in the family wise alpha control.

2) Frequency tabulations will be provided for the percentages of participants within each outcome of IGA-BP per analysis visit. Additionally cumulative percentages (starting with the best outcome result) will be calculated. For participants who received rescue therapy, only assessments prior to or on the start date of rescue therapy will be considered.

Frequency tabulations will be provided of the percentage of participants that have achieved IGA-BP score of 0 while receiving efgartigimod PH20 SC or placebo and have been off OCS therapy for ≥8 weeks at week 36.

The same stratified CMH as for the primary endpoint will be performed.

All IGA-BP data will be listed.

[figure not shown]
3) Frequency tabulations will be provided of the percentage of participants that have achieved control of disease activity (CDA) while receiving efgartigimod PH20 SC or placebo and remain free of relapse through week 36.

The same stratified CMH as for the primary endpoint will be performed.

4) Frequency tabulations will be provided of the percentage of participants that have achieved CR while receiving efgartigimod PH20 SC or placebo and while receiving minimal OCS therapy for ≥8 weeks (CRmin) at week 36.

The same stratified CMH as for the primary endpoint will be performed.

5) Descriptive statistics will present the actual values and changes from baseline of the itch NRS 24-hour average score per analysis visit. For participants who received

rescue therapy, only assessments prior to or on the start date of rescue therapy will be considered.

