Changes from baseline in the 24-hour average itch NRS score will be analysed using a mixed-effect model for repeated measurements (MMRM). The least square means on changes from baseline at week 36 will be calculated as well at the other analysis visits (with no strict control of alpha of these). The MMRM model will include treatment by visit and baseline value by visit interaction terms, and the two stratification factors as covariates. Within-subject correlation will be modeled using the R matrix. With 13 post-baseline visits during the treatment-phase, a standard unstructured covariance matrix would require 91 variance parameters. Therefore, a modified unstructured covariance matrix (UN) will be used: ANTE(1).

Least square means, SE, and 95% 2-sided CI for placebo and efgartigimod will be reported by analysis visit, along with LS means of the between-arm difference including also with SE, 95% 2-sided CI, and 2-sided p-value. If the default Newton-Raphson algorithm used by SAS PROC MIXED fails to converge, the following will be tried to avoid lack of convergence while maintaining an unstructured variance:

The Fisher scoring algorithm (via the SCORING = 5 option of the PROC MIXED statement) will be used to obtain the initial values of covariance parameters. In the rare case where the above fails, the following covariance structures will be tested for convergence (in order): toeph, arh(1), csh, toep, ar(1) and cs).

[figure not shown]
All itch NRS data will be listed.

Subgroup tables will be created for all key secondary endpoints (not for supplementary analysis).

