4.1.5 Fixed-Sequence testing procedure

The fixed-sequence testing procedure will only apply for the analysis of study Part B.

To control the type I error for the primary and secondary endpoints (alpha controlled), the primary efficacy endpoint will be tested at the 5% 2-sided alpha level and will act as gatekeeper for the testing of the key secondary endpoints. The primary endpoint and secondary endpoints will be tested in a strict hierarchical order as per the algorithm of section 1.4.3.2 to control the type I error.

The individual per-endpoint tables will only show unadjusted p-values. A fixed-sequence testing procedure table will be produced. This table will show both unadjusted p-values and p-values adjusted for multiplicity. For a given endpoint, the adjusted-for-multiplicity p-value is calculated as the maximum between its unadjusted p-value and the highest of all unadjusted p-values tested before.

- Primary endpoint: the proportion of participants who are in CR while receiving efgartigimod PH20 SC or placebo and have been off OCS therapy for ≥8 weeks at week 36 using a 'composite strategy' approach
- Secondary endpoints:
 - NCOD using 'while on treatment strategy' approach
 - Proportion of participants achieving IGA-BP score of 0 while receiving efgartigimod PH20 SC or placebo and have been off OCS therapy for ≥8 weeks at week 36 using a 'composite strategy' approach
 - Proportion of participants achieving control of disease activity (CDA) while receiving efgartigimod PH20 SC or placebo and remain free of relapse through week 36 using a 'composite strategy' approach
 - Proportion of participants achieving CR while receiving efgartigimod PH20 SC or placebo and have been receiving minimal OCS therapy for ≥8 weeks at week 36 using a 'composite strategy' approach
 - Change from baseline to week 36 in the 24-hour average Itch NRS score using a 'treatment policy' approach

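### The Part B order of the key secondary endpoints is set by 2-sided interim p-values with no direction criterion, so an endpoint trending against efgartigimod can be ranked ahead of, and block, one trending in favour

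*SAP*

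**What the plan says.** The ordering rule is in SAP section 1.4.3.2: "The endpoints will be sorted in ascending order (i.e., smallest p-value first, largest p-value last"). The same section makes the resulting order the one used in the Part B fixed sequence. It does not itself state whether the p-values are 1- or 2-sided. SAP section 1.4.3.1 supplies that by having the five endpoints analysed at the interim as in section 4.1.3, where every analysis is 2-sided:

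- **IGA-BP 0 off OCS, CDA without relapse, and CR on minimal OCS** use the primary endpoint's stratified CMH, reported with an "exact 95% CI and 2-sided p-value from the CMH association test" (SAP 4.1.2.3, reused in 4.1.3.2).
- **NCOD** uses an ANCOVA with "95% 2-sided CI, and 2-sided p-value" (SAP 4.1.3.2).
- **Average itch NRS** uses an MMRM giving "LS means of the between-arm difference including also with SE, 95% 2-sided CI, and 2-sided p-value" (SAP 4.1.3.2).

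For Part B, SAP section 4.1.5 has the endpoints "tested in a strict hierarchical order as per the algorithm of section 1.4.3.2 to control the type I error". The adjusted p-value is "the maximum between its unadjusted p-value and the highest of all unadjusted p-values tested before". Protocol section 9.1.1 likewise requires significance at each rank before the next is tested.

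Two passages leave room for change without giving a criterion. SAP section 1.2 says "The proposed order of the key secondary endpoints for part B may be adjusted based on the results obtained in the IA", and protocol section 4.1.1 says the order "may be adjusted based on the results obtained from the part A interim analysis". Protocol section 9.1.1 also lets a different multiplicity strategy be proposed after the interim.

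**The concern.** A 2-sided p-value measures distance from no effect in either direction. It does not measure evidence of benefit. Sorting on it treats a strong trend towards placebo as a reason to test that endpoint early. The evident aim of the sort is to test the most promising endpoints first, and for wrong-direction endpoints it does the reverse.

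With about 20 participants per arm in Part A, an endpoint with little or no true effect can easily point the wrong way by chance. If it does so strongly enough, it moves up the order. In Part B it will then probably fail, and every endpoint below it loses its chance of a formal claim. What is at stake is power for the key secondary claims.

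**Working it through.** **The plan's own figure.** The ordering rule has no stated operating characteristic. The nearest stated figure is 120 Part B participants for more than 90% power (protocol 9.5). The protocol's response rates are redacted, so I used the SAP's simulation rates of 20% vs 50% (SAP 1.4.2.1). At 60 per arm, the normal approximation gives 94.1% and Fisher's exact test 91.3%, both consistent with the statement.

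**Worked example, 20 per arm.** The statistic is the unstratified CMH, z = (a − m/2)/√v with v = n²·m·(N − m)/[N²(N − 1)]. Here a is efgartigimod responders, m all responders, n = 20 and N = 40. For 7 vs 14, m = 21 and v = 400·21·19/(1600·39) = 2.558, so z = (7 − 10.5)/1.599 = −2.19.

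| Responders, efgartigimod vs placebo | 2-sided p | SAP rank | 1-sided p for benefit | Directional rank |
|---|---|---|---|---|
| 7 vs 14 | 0.029 | 1 | 0.986 | 5 |
| 10 vs 4 | 0.050 | 2 | 0.025 | 1 |
| 11 vs 6 | 0.114 | 3 | 0.057 | 2 |
| 12 vs 8 | 0.212 | 4 | 0.106 | 3 |
| 11 vs 8 | 0.348 | 5 | 0.174 | 4 |

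Under the SAP rule the adverse endpoint is tested first. If its true effect is nil, it reaches 2-sided significance in Part B 5% of the time (2.5% in efgartigimod's favour). The other four are then blocked about 95% of the time.

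**Simulation inputs.**
- Six equicorrelated z-statistics (the primary and five key secondaries) at the interim (40 participants) and, independently, in Part B (120 participants, means multiplied by √3).
- Primary: 90% Part B power means an expected z of 1.960 + 1.282 = 3.242, so the interim mean is 3.242/√3 = 1.87.
- Continuation: SAP 1.4.1.4 stops if UL90 is at or below 30%. SE = √(0.2·0.8/20 + 0.5·0.5/20) = 0.143, so continuing needs a difference above 0.30 − 1.282·0.143 = 0.117, or z of about 0.81. I used 0.82.
- Gate: Part B primary z > 1.96. About 77% of trials started pass both conditions, and results are for those trials.
- Key secondaries tested in sequence at z > 1.96, ordered by |z| (SAP rule) or signed z (directional). 400,000 trials per scenario.
- Key secondary effects and the correlation are assumptions.

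**Results at correlation 0.5.**

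| Scenario: interim mean z of the five | Wrong-direction ahead of right-direction | Wrong-direction first | Mean claims, SAP vs directional | Trials losing at least one claim |
|---|---|---|---|---|
| 1: 1.87, 1.5, 1.5, 1.0, 0 | 24% | 5% | 2.00 vs 2.23 | 13% |
| 2: 1.5, 1.5, 1.5, 0, 0 | 37% | 9% | 1.54 vs 1.83 | 16% |
| 3: 1.5, 1.5, 1.5, 1.0, 0.5 | 17% | 3% | 1.92 vs 2.00 | 5% |
| 4: 1.87, 1.87, 1.5, 1.5, 1.0 | 7% | 1% | 3.01 vs 3.03 | 2% |
| 5: all 1.87 | 2% | 0.2% | no loss | – |

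Over correlations 0.3 to 0.7 the mean loss is about 0.20–0.26 in scenario 1, 0.25–0.31 in 2, 0.07–0.09 in 3 and 0.02 in 4. Per trial started it is 0.18 in scenario 1 and 0.22 in 2. Repeat runs agree to within about 0.01 in mean claims.

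**The case against.** Four points can be made against the concern.

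**The continuation rule is generous.** SAP 1.4.1.4 gives a clear *Go* only if LL80 also exceeds 10%. That needs a difference above 0.10 + 0.842·0.143 = 0.22, or z of about 1.54. Between the two cut-offs the outcome is *Consider*, and the key secondaries are reviewed before a decision. Counting only *Go* trials, scenario 1 gives 2.09 vs 2.23 claims (loss 0.14) with 8.5% of trials losing one, and scenario 2 gives 1.64 vs 1.82 with 11%. This stands as a lower figure, since some *Consider* trials would continue. It does not remove the loss, because that review decides whether to go on and does not set the order.

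**The material cases assume a null endpoint.** This also stands. IGA-BP 0 off OCS shares the primary's off-OCS condition, and SAP 4.1.3.1 counts participants in CR off OCS for at least 8 weeks as CRmin responders. A null effect on either beside a working primary is unlikely. The risk sits mainly with NCOD, CDA without relapse, and itch. Allowing for that overlap, with itch alone null, left the loss near 0.2.

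**The order can be corrected later.** The protocol and SAP do allow changes after the interim. However, none of those provisions mentions direction, and section 1.4.3.2 lacks the allowance for deviation that SAP 1.4.1.4 gives the futility rule. An ad hoc correction by people who have seen the data is weaker than a stated rule.

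**It touches only secondary claims.** True, and this limits its severity.

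**Conclusion.** The concern holds. Followed as written, the SAP can promote an endpoint because it trended against efgartigimod, and that endpoint can then block claims that would have succeeded. The textual finding is firm.

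The size is conditional. The expected loss is about 0.2 to 0.3 key secondary claims when one or two of the five have no true effect (0.14 to 0.18 if only clear *Go* trials continue), and 0.08 or less when all five work. These figures rest on assumed effects, a common correlation, a normal approximation and an approximate futility cut-off. They also treat interim results as full week-36 data, although SAP 1.4.1.2 substitutes the last visit for participants still on treatment.

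Part B type I error is not affected, because the order comes from separate Part A participants. The change should be made, but it does not threaten the trial's primary conclusion.

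**What to change.** In SAP section 1.4.3.2, rank the five endpoints by the 1-sided p-value for efgartigimod benefit, smallest first (equivalently, by signed test statistic, largest benefit first). State the favourable direction for each: lower NCOD, a higher proportion for the three responder endpoints, and a larger reduction in itch.

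If the interim has already been run, the resulting order should be checked for wrong-direction endpoints. The unblinded statistician or the Adaptation Committee should do this, since SAP 1.4.4.2 and 1.4.4.4 keep interim results within that group. The final order should be documented before Part B is unblinded.

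The cost is one sentence and a short list of signs, with no change in alpha or sample size. The directional sort did not lose power on average in any scenario simulated, although in up to roughly 2–3% of individual trials the SAP order happened to win more claims.

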1.4.4 Data access plan

To preserve the integrity of Part A data, the dissemination of IA results will be limited. In this section, further details on this are given.

1.4.4.1 Personnel who will perform the interim analyses

The biometrics contract research organization (SGS) will appoint a separate unblinded biostatistician to perform the unblinded IA and release it to the recipients as defined below.

The identity of this person will be documented and archived in the biometrics ARGX-113-2009 eTMF before executing the IA.

1.4.4.2 Personnel who will have access to interim results

Results of the IA of part A will not be shared with sites personnel and investigators. Access to the results of the IA will also be restricted within the sponsor. An unblinded Adaptation Committee (AC) will be established. No permanent members of the ARGX-113-2009 Clinical Trial Team (CTT) will be part of the AC. No members outside the AC will have access to unblinded data.

The exact list of members of the AC will be documented and archived in the Argenx ARGX-113-2009 eTMF (Veeva) before executing the IA.

1.4.4.3 ACCESS CONTROL

SGS will install a secured transfer folder with only access for the unblinded biostatistician and the unblinded AC.

SGS	Statistical Analysis Plan	
ARGX-113-2009	Final and Interim Analysis	Final 4.0 of 04NOV2024

